## 9.5 CAEPRS

### 9.5.1 Comprehensive Adverse Events and Potential Risks list (CAEPR) for Vemurafenib (Zelboraf, RO5185426, NSC 761431)

The Comprehensive Adverse Events and Potential Risks list (CAEPR) provides a single list of reported and/or potential adverse events (AE) associated with an agent using a uniform presentation of events by body system. In addition to the comprehensive list, a subset, the Specific Protocol Exceptions to Expedited Reporting (SPEER), appears in a separate column and is identified with bold and italicized text. This subset of AEs (SPEER) is a list of events that are protocol specific exceptions to expedited reporting to NCI (except as noted below). Refer to the 'CTEP, NCI Guidelines: Adverse Event Reporting Requirements'

for further clarification. *Frequency is provided based on 5019 patients.* Below is the CAEPR for Vemurafenib (Zelboraf, RO5185426).

**NOTE:** Report AEs on the SPEER **ONLY IF** they exceed the grade noted in parentheses next to the AE in the SPEER. If this CAEPR is part of a combination protocol using multiple investigational agents and has an AE listed on different SPEERs, use the lower of the grades to determine if expedited reporting is required.

Version 2.1, April 2, 2019

Adverse Events with Possible Relationship to Vemurafenib (Zelboraf, RO5185426) (CTCAE 5.0 Term) [n= 5019]		
Likely (>20%)	Less Likely (<=20%)	Rare but Serious (<3%)
EYE DISORDERS		
		Uveitis
GASTROINTESTINAL DISORDERS		
	Abdominal pain	
	Constipation	
	Diarrhea	
Nausea		
		Pancreatitis
	Vomiting	
GENERAL DISORDERS AND ADMINISTRATION SITE CONDITIONS		
	Edema limbs	
Fatigue		
	Fever	
HEPATOBIILIARY DISORDERS		
		Hepatic failure
IMMUNE SYSTEM DISORDERS		
	Allergic reaction*	
		Anaphylaxis
INFECTIONS AND INFESTATIONS		
	Folliculitis	
	Infections and infestations - Other (nasopharyngitis)	
INJURY, POISONING AND PROCEDURAL COMPLICATIONS		
		Injury, poisoning and procedural complications - Other (radiation injury) 
INVESTIGATIONS		
	Alanine aminotransferase increased	
	Alkaline phosphatase increased	
	Aspartate aminotransferase increased	
	Blood bilirubin increased	
	Creatinine increased	
	Electrocardiogram QT corrected interval prolonged	
	GGT increased	

Adverse Events with Possible Relationship to Vemurafenib (Zelboraf, RO5185426) (CTCAE 5.0 Term) [n= 5019]		
Likely (>20%)	Less Likely (<=20%)	Rare but Serious (<3%)
	Neutrophil count decreased*	
	Serum amylase increased*	
	Weight loss	
METABOLISM AND NUTRITION DISORDERS		
	Anorexia	
MUSCULOSKELETAL AND CONNECTIVE TISSUE DISORDERS		
Arthralgia		
	Back pain	
	Musculoskeletal and connective tissue disorder - Other (Dupuytren's contracture and plantar fibromatosis)*	
	Myalgia	
	Pain in extremity	
NEOPLASMS BENIGN, MALIGNANT AND UNSPECIFIED (INCL CYSTS AND POLYPS)		
	Skin papilloma	
	Treatment related secondary malignancy - Cutaneous squamous cell carcinoma (SCC), including keratocanthoma or mixed keratocanthoma subtype	
		Treatment related secondary malignancy - including non-cutaneous squamous cell carcinoma, melanoma and others
		Treatment related secondary malignancy - progression of RAS mutant tumors
NERVOUS SYSTEM DISORDERS		
	Dizziness	
	Dysgeusia	
		Facial nerve disorder
	Headache	
	Peripheral motor neuropathy*	
	Peripheral sensory neuropathy*	
RENAL AND URINARY DISORDERS		
	Acute kidney injury*	
		Renal and urinary disorders - Other (renal failure)
RESPIRATORY, THORACIC AND MEDIASTINAL DISORDERS		
	Cough	
SKIN AND SUBCUTANEOUS TISSUE DISORDERS		
Alopecia		
	Dry skin	

Adverse Events with Possible Relationship to Vemurafenib (Zelboraf, RO5185426) (CTCAE 5.0 Term) [n= 5019]		
Likely (>20%)	Less Likely (<=20%)	Rare but Serious (<3%)
Hyperkeratosis		
	Palmar-plantar erythrodysesthesia syndrome	
Photosensitivity		
	Pruritus	
Rash maculo-papular		
		Skin and subcutaneous tissue disorders - Other (DRESS; drug reaction with eosinophilia and systemic symptoms)
	Skin and subcutaneous tissue disorders - Other (including actinic keratosis, keratosis pilaris)	
	Skin and subcutaneous tissue disorders - Other (panniculitis)*	
		Stevens-Johnson syndrome
		Toxic epidermal necrolysis
	Urticaria*	

\*Denotes adverse events that are <3%

This table will be updated as the toxicity profile of the agent is revised. Updates will be distributed to all Principal Investigators at the time of revision. The current version can be obtained by contacting

Your name, the name of the investigator, the protocol and the agent should be included in the e-mail.

Radiation injury includes recall phenomenon and radiation sensitization. Observed events include radiation dermatitis and skin necrosis; radiation pneumonitis, hepatitis, and esophagitis; and radiation proctitis and cystitis.

**Adverse events reported on vemurafenib (Zelboraf, RO5185426) trials, but for which there is insufficient evidence to suggest that there was a reasonable possibility that vemurafenib (Zelboraf, RO5185426) caused the adverse event:**

**BLOOD AND LYMPHATIC SYSTEM DISORDERS** - Anemia

**CARDIAC DISORDERS** - Heart failure; Pericardial effusion; Ventricular arrhythmia

**EAR AND LABYRINTH DISORDERS** - Ear pain; Vertigo

**EYE DISORDERS** - Blurred vision; Dry eye; Eye disorders - Other (chorioretinopathy); Eye disorders - Other (ocular hyperemia); Eye disorders - Other (retinal vein occlusion); Eye disorders - Other (visual disturbance); Eye disorders - Other (vitritis); Eye pain; Floaters; Photophobia; Scleral disorder; Watery eyes

**GASTROINTESTINAL DISORDERS** - Dry mouth; Dyspepsia; Dysphagia; Flatulence; Gastritis; Gastroesophageal reflux disease; Mucositis oral

**GENERAL DISORDERS AND ADMINISTRATION SITE CONDITIONS** - Chills; Edema face; Multi-organ failure; Non-cardiac chest pain; Pain

**HEPATOBIILIARY DISORDERS** - Hepatobiliary disorders - Other (cholestasis)

**INFECTIONS AND INFESTATIONS** - Conjunctivitis

**INJURY, POISONING AND PROCEDURAL COMPLICATIONS** - Bruising

**INVESTIGATIONS** - Activated partial thromboplastin time prolonged; Cholesterol high; Lipase increased; Lymphocyte count decreased; Platelet count decreased

**METABOLISM AND NUTRITION DISORDERS** - Dehydration; Hypercalcemia; Hyperglycemia; Hyperkalemia; Hypertriglyceridemia; Hyperuricemia; Hypoalbuminemia; Hypocalcemia; Hypoglycemia; Hypokalemia; Hypomagnesemia; Hyponatremia; Hypophosphatemia; Metabolism and nutrition disorders - Other (blood phosphorus level increased)

**MUSCULOSKELETAL AND CONNECTIVE TISSUE DISORDERS** - Arthritis; Generalized muscle weakness; Joint range of motion decreased; Muscle cramp; Neck pain

**NEOPLASMS BENIGN, MALIGNANT AND UNSPECIFIED (INCL CYSTS AND POLYPS)** - Neoplasms benign, malignant and unspecified (incl cysts and polyps) - Other (adenomatous colon polyp)

**NERVOUS SYSTEM DISORDERS** - Intracranial hemorrhage; Lethargy; Seizure; Somnolence; Tremor

**PSYCHIATRIC DISORDERS** - Anxiety; Confusion; Depression; Insomnia; Irritability

**RENAL AND URINARY DISORDERS** - Hemoglobinuria; Proteinuria; Urinary frequency; Urinary incontinence

**REPRODUCTIVE SYSTEM AND BREAST DISORDERS** - Erectile dysfunction; Premature menopause

**RESPIRATORY, THORACIC AND MEDIASTINAL DISORDERS** - Allergic rhinitis; Bronchopulmonary hemorrhage; Dyspnea; Epistaxis; Nasal congestion; Pharyngolaryngeal pain; Postnasal drip; Respiratory failure; Voice alteration

**SKIN AND SUBCUTANEOUS TISSUE DISORDERS** - Erythema multiforme; Hyperhidrosis; Nail changes; Nail discoloration; Skin and subcutaneous tissue disorders - Other (acrochordon); Skin and subcutaneous tissue disorders - Other (demal cyst); Skin and subcutaneous tissue disorders - Other (madarosis)

**VASCULAR DISORDERS** - Flushing; Hot flashes; Hypertension; Hypotension; Thromboembolic event; Vasculitis

**Note:** Vemurafenib (Zelboraf, RO5185426) in combination with other agents could cause an exacerbation of any adverse event currently known to be caused by the other agent, or the combination may result in events never previously associated with either agent.

## 9.5.2 Comprehensive Adverse Events and Potential Risks list (CAEPR) for Cobimetinib (RO5514041, GDC0973, NSC 781257)

The Comprehensive Adverse Events and Potential Risks list (CAEPR) provides a single list of reported and/or potential adverse events (AE) associated with an agent using a uniform presentation of events by body system. In addition to the comprehensive list, a subset, the Specific Protocol Exceptions to Expedited Reporting (SPEER), appears in a separate column and is identified with bold and italicized text. This subset of AEs (SPEER) is a list of events that are protocol specific exceptions to expedited reporting to NCI (except as noted below). Refer to the 'CTEP, NCI Guidelines: Adverse Event Reporting Requirements'

for further clarification. *Frequency is provided based on 274 patients.* Below is the CAEPR for Cobimetinib (RO5514041, GDC0973).

**NOTE:** Report AEs on the SPEER **ONLY IF** they exceed the grade noted in parentheses next to the AE in the SPEER. If this CAEPR is part of a combination protocol using multiple

investigational agents and has an AE listed on different SPEERs, use the lower of the grades to determine if expedited reporting is required.

**Version 2.2, March 25, 2020^1**

Adverse Events with Possible Relationship to Cobimetinib (RO5514041, GDC0973) (CTCAE 5.0 Term) [n= 274]		
Likely (>20%)	Less Likely (<=20%)	Rare but Serious (<3%)
BLOOD AND LYMPHATIC SYSTEM DISORDERS		
	Anemia	
CARDIAC DISORDERS		
		Cardiac disorders - Other (cardiomyopathy)
		Cardiac disorders - Other (left ventricular dysfunction)
		Heart failure
EYE DISORDERS		
	Eye disorders - Other (chorioretinopathy) 	
	Eye disorders - Other (eye disorders) 	
		Eye disorders - Other (retinal vein occlusion) 
	Retinal detachment	
GASTROINTESTINAL DISORDERS		
Diarrhea		
	Mucositis oral	
Nausea		
Vomiting		
GENERAL DISORDERS AND ADMINISTRATION SITE CONDITIONS		
	Chills	
Fatigue		
	Fever 	
Generalized edema 		
IMMUNE SYSTEM DISORDERS		
	Allergic reaction	
INVESTIGATIONS		
	Alanine aminotransferase increased 	
	Alkaline phosphatase increased 	
	Aspartate aminotransferase increased 	
CPK increased		
	Ejection fraction decreased	
	GGT increased 	
METABOLISM AND NUTRITION DISORDERS		
	Anorexia	
	Dehydration	
	Hyperglycemia	
	Hypokalemia	
	Hyponatremia	

Adverse Events with Possible Relationship to Cobimetinib (RO5514041, GDC0973) (CTCAE 5.0 Term) [n= 274]		
Likely (>20%)	Less Likely (<=20%)	Rare but Serious (<3%)
	Hypophosphatemia	
MUSCULOSKELETAL AND CONNECTIVE TISSUE DISORDERS		
		Rhabdomyolysis
NEOPLASMS BENIGN, MALIGNANT AND UNSPECIFIED (INCL CYSTS AND POLYPS)		
		Neoplasms benign, malignant and unspecified (incl cysts and polyps) - Other (new primary malignancies, cutaneous and non-cutaneous) 
NERVOUS SYSTEM DISORDERS		
	Dizziness	
	Headache	
RESPIRATORY, THORACIC AND MEDIASTINAL DISORDERS		
		Pneumonitis
SKIN AND SUBCUTANEOUS TISSUE DISORDERS		
	Dry skin	
	Photosensitivity 	
	Pruritus	
	Rash acneiform	
Rash maculo-papular 		
VASCULAR DISORDERS		
	Vascular disorders - Other (hemorrhage) 	

This table will be updated as the toxicity profile of the agent is revised. Updates will be distributed to all Principal Investigators at the time of revision. The current version can be obtained by contacting [REDACTED] Your name, the name of the investigator, the protocol and the agent should be included in the e-mail.

Observed in combination with Vemurafenib.

Includes photopsia, blurred vision, vitreous floaters.

Includes peripheral edema, periorbital edema, edema, and facial edema.

Includes rash, dermatitis acneiform, rash pruritic, rash generalized dermatitis, exfoliative rash, rash erythematous, and rash maculo-papular.

Hemorrhage includes cerebral hemorrhage, contusion, ecchymosis, epistaxis, gastrointestinal hemorrhage, hematuria, rectal hemorrhage, retinal hemorrhage, and vaginal hemorrhage.

**Adverse events reported on cobimetinib (RO5514041, GDC0973) trials, but for which there is insufficient evidence to suggest that there was a reasonable possibility that cobimetinib (RO5514041, GDC0973) caused the adverse event:**

**CARDIAC DISORDERS** - Atrial fibrillation; Cardiac arrest; Cardiac disorders - Other (cardiac ventricular thrombosis); Pericardial effusion

**EAR AND LABYRINTH DISORDERS** - Ear pain

**EYE DISORDERS** - Eye disorders - Other (retinal disorder); Vision decreased

**GASTROINTESTINAL DISORDERS** - Abdominal pain; Colitis; Constipation; Dysphagia; Ileus; Lower gastrointestinal hemorrhage; Small intestinal perforation

**GENERAL DISORDERS AND ADMINISTRATION SITE CONDITIONS** - Death NOS; Non-cardiac chest pain

**HEPATOBIILIARY DISORDERS** - Hepatobiliary disorders - Other (autoimmune hepatitis); Hepatobiliary disorders - Other (bile duct obstruction); Hepatobiliary disorders - Other (cholangitis)

**INFECTIONS AND INFESTATIONS** - Catheter related infection; Gallbladder infection; Infections and infestations - Other (diverticulitis); Lung infection; Paronychia; Sepsis; Skin infection; Thrush; Urinary tract infection

**INVESTIGATIONS** - Blood bilirubin increased; Blood lactate dehydrogenase increased; Electrocardiogram QT corrected interval prolonged; Lymphocyte count decreased; Neutrophil count decreased; Platelet count decreased; White blood cell decreased

**METABOLISM AND NUTRITION DISORDERS** - Hypercalcemia; Hypomagnesemia

**MUSCULOSKELETAL AND CONNECTIVE TISSUE DISORDERS** - Arthralgia; Back pain; Neck pain; Pain in extremity

**NEOPLASMS BENIGN, MALIGNANT AND UNSPECIFIED (INCL CYSTS AND POLYPS)** - Neoplasms benign, malignant and unspecified (incl cysts and polyps) - Other (malignant neoplasm progression); Tumor hemorrhage

**NERVOUS SYSTEM DISORDERS** - Encephalopathy; Facial muscle weakness; Nervous system disorders - Other (immune-mediated encephalitis); Nervous system disorders - Other (intracranial pressure increased); Nervous system disorders - Other (7th nerve palsy); Somnolence; Syncope

**RESPIRATORY, THORACIC AND MEDIASTINAL DISORDERS** - Cough; Dyspnea; Epistaxis; Nasal congestion; Oropharyngeal pain; Pneumothorax; Respiratory failure

**SKIN AND SUBCUTANEOUS TISSUE DISORDERS** - Eczema; Hyperkeratosis

**SURGICAL AND MEDICAL PROCEDURES** - Surgical and medical procedures - Other (medical device change)

**VASCULAR DISORDERS** - Hypertension; Thromboembolic event

**Note:** Cobimetinib (RO5514041, GDC0973) in combination with other agents could cause an exacerbation of any adverse event currently known to be caused by the other agent, or the combination may result in events never previously associated with either agent.

## 10.0 DRUG INFORMATION

Product complaints: A product complaint is any written or oral information received from a complainant that alleges deficiencies related to identity, quality, safety, strength, purity, reliability, durability, effectiveness or performance of a product after it has been released and distributed to the commercial market or clinical trial. Please email any complaints related to the study agents to

[REDACTED]

**10.1 Vemurafenib (Zelboraf®) (RO5185426, PLX4032) (NSC#761431, IND EXEMPT)***Investigator Brochure Availability*

The investigator brochure for Vemurafenib (Zelboraf®) (RO5185426, PLX4032) may be obtained by contacting the Alliance Central Protocol Operations Program office at [REDACTED]

*Procurement*

Vemurafenib will be provided by F. Hoffmann-LA Roche LTD and distributed by RxCrossroads by McKesson. Use the vemurafenib order form on the A071601 study page.

Investigators ordering and/or dispensing supplied agents at any time for study treatment must be currently registered with PMB, DCTD, NCI. A registered investigator must co-sign for other non-registered personnel prescribing the supplied agents.

At the end of the trial, any expired or remaining supplies should be destroyed according to institutional procedure.

*Formulation*

Vemurafenib is available as 240 mg film coated tablets. Each vemurafenib tablet contains 240 mg vemurafenib and inactive ingredients include: Tablet core: hypromellose acetate succinate, croscarmellose sodium, colloidal silicon dioxide, magnesium stearate, and hydroxypropyl cellulose. Coating: pinkish white: poly (vinyl alcohol), titanium dioxide, polyethylene glycol 3350, talc, and iron oxide red. Vemurafenib is available as bottles of 112 tablets.

*Storage and stability*

Store at room temperature 20°C to 25 °C (68 °F to 77 °F); excursions permitted between 15°C and 30°C (59°F and 86°F).

*Administration*

Vemurafenib is taken orally twice daily with or without food. Doses should be administered in the morning and evening, approximately 12 hours apart. If a dose of vemurafenib is missed, it can be taken up to 4 hours prior to the next scheduled dose. If vomiting occurs after a dose is taken, do not take an additional dose; continue with the next scheduled dose. Swallow tablets whole with a glass of water, do not crush or chew.

*Drug Accountability*

The NCI Investigational Agent Accountability Record Form for Oral Agents should be utilized.

*Drug interactions*

Vemurafenib is a substrate of CYP3A4 based on in vitro data; therefore, co-administration of strong CYP3A4 inhibitors or inducers may alter vemurafenib concentrations. Avoid the co-administration of vemurafenib with strong CYP3A4 inhibitors (i.e. ketoconazole, itraconazole, clarithromycin, atazanavir, nefazodone, saquinavir, telithromycin, ritonavir, indinavir, nelfinavir, voriconazole) or strong inducers (i.e. phenytoin, carbamazepine, rifampin, rifabutin, rifapentine, phenobarbital) and replace these drugs with alternatives when possible.

Vemurafenib may increase concentrations of CYP1A2 substrates. Co-administration of tizanidine, a sensitive CYP1A2 substrate, increased tizanidine systemic exposure by 4.7-fold. Avoid the concomitant use of vemurafenib and CYP1A substrates with a narrow therapeutic window. If coadministration cannot be avoided, monitor closely for toxicities and consider a dose reduction of CYP1A2 substrates.

Co-administration of vemurafenib with digoxin, a sensitive P-glycoprotein substrate, increased digoxin systemic exposure by 1.8-fold. Avoid the concurrent use of P-glycoprotein substrates

known to have narrow therapeutic indices. If use of these medications is unavoidable, consider a dose reduction of the P-glycoprotein substrate with narrow therapeutic indices.

#### *Pharmacokinetics*

Absorption: Bioavailability not determined.

Distribution: Vd ~ 106L. Plasma protein binding is > 99% to albumin and  $\alpha$ 1-acid glycoprotein.

Metabolism: Following oral administration of 960 mg of vemurafenib, mean data showed that vemurafenib and its metabolites represented 95% and 5% of the components in plasma over 48 hours respectively.

Half-life, elimination: 57 hours (range: 30 to 120 hours)

Time to peak: ~ 3 hours

Excretion: Feces ~94%, urine ~1%

#### *Adverse events*

See CAEPR in [Section 9.5.1](#).

#### *Nursing guidelines*

- Instruct patients to take doses by mouth, approximately 12 hours apart in am and pm. Can be taken regardless of food intake. If patient misses a dose by more than 4 hours, do not make up that dose. Swallow whole, do not crush or chew.
- Instruct patient to report any rash, which is common. Patients that have rash and/or blisters accompanied by fever and/or oral or anogenital lesions, should be seen emergently to rule out Steven's Johnson Syndrome.
- Diarrhea and nausea are common. Treat symptomatically and monitor for effectiveness.
- Photosensitivity is common and can be quite severe with blistering burns, with little sun exposure. Instruct patients to photo protect with sunscreen, protective clothing, and avoidance of intense sun exposure.
- Warn patients of possibility of secondary skin cancers. Instruct patients to report any new lesions to study team immediately.
- Warn patient of possible alopecia.
- Monitor LFT's, especially in combination therapy.
- Agent may cause arthralgias. Treat symptomatically and monitor for effectiveness.
- Hand-foot syndrome has been seen. Instruct patients to report any pain and/or redness, thickening of skin and/or skin peeling of hands or feet to the study team.
- Agent causes QTc prolongation. Instruct patients to discuss any new medications with the study team, prior to starting such agents.
- Agent can cause peripheral edema.
- Rarely ocular toxicity can occur including retinitis, uveitis, and retinal vein occlusion. Instruct patients to report any vision changes and/or eye pain to the study team.

## **10.2 Cobimetinib (Cotellic®) (RO5514041) (NSC#781257, IND EXEMPT)**

#### *Investigator Brochure Availability*

The investigator brochure for Cobimetinib (Cotellic®) (RO5514041) may be obtained by contacting the Alliance Central Protocol Operations Program office at [REDACTED]

### *Procurement*

Cobimetinib will be provided by F. Hoffmann-LA Roche LTD and distributed by RxCrossroads by McKesson. Use the cobimetinib order form on the A071601 study page.

Investigators ordering and/or dispensing supplied agents at any time for study treatment must be currently registered with PMB, DCTD, NCI. A registered investigator must co-sign for other non-registered personnel prescribing the supplied agents.

At the end of the trial, any expired or remaining supplies should be destroyed according to institutional procedure.

### *Formulation*

Cobimetinib is available as 20 mg film coated tablets. Each cobimetinib tablet contains 22 mg cobimetinib fumarate (which corresponds to 20 mg of the cobimetinib free base) and the following inactive ingredients: Tablet core: microcrystalline cellulose, lactose monohydrate, croscarmellose sodium, magnesium stearate. Coating: polyvinyl alcohol, titanium dioxide, polyethylene glycol 3350, talc. Cobimetinib is available as bottles of 63 tablets.

### *Storage and stability*

Store at room temperature at 59°F–77°F (15°C–25°C).

### *Administration*

Cobimetinib is taken orally once daily Days 1 through 21 of a 28-day cycle with or without food. If a dose of cobimetinib is missed (i.e., 6 hours or more late for cobimetinib), do not make up that dose; resume dosing with the next scheduled dose.

### *Drug Accountability*

The NCI Investigational Agent Accountability Record Form for Oral Agents should be utilized.

### *Drug interactions*

Coadministration of cobimetinib with itraconazole (a strong CYP3A4 inhibitor) increased cobimetinib systemic exposure by 6.7-fold. Avoid concurrent use of cobimetinib and strong or moderate CYP3A inhibitors.

Coadministration of cobimetinib with a strong CYP3A inducer may decrease cobimetinib systemic exposure by more than 80% and reduce its efficacy. Avoid concurrent use of cobimetinib and strong or moderate CYP3A4 inducers including but not limited to carbamazepine, efavirenz, phenytoin, rifampin, and St. John's wort.

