### Key Registration Eligibility Criteria (see [Section 3.3](#))

- Histologically proven papillary craniopharyngioma as documented by central path review
- Measureable disease, defined as  $\geq 1\text{cm}^3$  present on imaging
- Surgery completed  $\geq 21$  days from registration.
- Cohort A: No prior therapy other than surgery. Progressive disease allowed but not required.
- Cohort B: Prior radiation therapy and progressive disease required. Completion of RT  $\geq 14$  days from registration.
- No prior treatment with BRAF or MEK inhibitors
- Steroid dosing stable for  $\geq 4$  days
- Non pregnant and non nursing
- Age  $\geq 18$  years
- ECOG Performance Status  $\leq 2$
- No comorbid conditions as outlined in [Section 3.3.6](#).
- No CYP3A4 inducers and inhibitors and CYP1A2 substrates within 14 days of registration

[figure not shown]

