**Please refer to the full protocol text for a complete description of the eligibility criteria and treatment plan.**

Study components allowed to be completed at non-registering institutions: Surgery for patients enrolled on Cohort A. Surgery and Radiation for patients enrolled Cohort B. Supporting documentation must be submitted per [Section 6.1.1](#) even if performed at non-registering institution.

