### **3.3.7 Concomitant medications**

- Chronic concomitant treatment with strong CYP3A4 inducers or CYP3A4 inhibitors is not allowed. Patients must discontinue the drug at least 14 days prior to study registration. See [Sections 8.1.9](#) and [8.1.10](#) for more information.
- Chronic concomitant treatment with CYP1A2 substrate is not allowed. Patients must discontinue the drug at least 14 days prior to study registration. See [Section 8.1.11](#) for more information.

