#### 8.1.10 CYP3A4 inducers

Chronic concomitant treatment with strong inducers of CYP3A4 is not allowed during on this trial. The following drugs are EXAMPLES of strong inducers of CYP3A4 and are not allowed during treatment with vemurafenib and cobimetinib.

- Rifampin
- Carbamazepine

Because lists of these agents are constantly changing, please consult and review any drugs for their potential to induce CYP3A4. Examples of resources that may be utilized include the product information for the individual concomitant drug in question, medical reference texts such as the Physicians' Desk Reference, the FDA website, or your local institution's pharmacist.

Investigators may provide patients with the wallet handout card provided [Appendix V](#).

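### The 20 mg rule for moderate CYP3A4 inhibitors gives no reduction to a patient already on 20 mg, two hormonal methods satisfy the contraception rule, and the inducer limits in 3.3.7 and 8.1.10 are narrower than in 10.2

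*Combined protocol and SAP*

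**What the plan says.** **Moderate inhibitors.** Section 8.1.9 bars chronic strong CYP3A4 inhibitors. It allows a moderate one for at most 14 days when it cannot be avoided, with cobimetinib set to 20 mg meanwhile and the previous dose resumed afterwards. Section 8.2.1 lists three cobimetinib levels, 60, 40 and 20 mg once daily, and nothing lower. Section 8.2 refers sites to the investigator's brochure or the study chair for further guidance.

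**Contraception.** Section 3.1 says that vemurafenib and cobimetinib may lower hormonal contraceptive concentrations, and for that reason asks for two methods. It lists four as appropriate: abstinence, oral contraceptives, implantable hormonal contraceptives and a double barrier. It asks physicians to discuss the methods before enrolment. Section 3.3.4 describes the treatment as teratogenic.

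**Inducers.** Section 3.3.7 reads "Chronic concomitant treatment with strong CYP3A4 inducers or CYP3A4 inhibitors is not allowed", with a 14-day washout. Section 8.1.10 reads "Chronic concomitant treatment with strong inducers of CYP3A4 is not allowed during on this trial", gives rifampin and carbamazepine as examples, and asks sites to "please consult and review any drugs for their potential to induce CYP3A4". For vemurafenib, 10.1 lists "strong inducers (i.e. phenytoin, carbamazepine, rifampin, rifabutin, rifapentine, phenobarbital) and replace these drugs with alternatives when possible". For cobimetinib, 10.2 is wider: "Avoid concurrent use of cobimetinib and strong or moderate CYP3A4 inducers including but not limited to carbamazepine, efavirenz, phenytoin, rifampin, and St. John's wort". The summary page has "No CYP3A4 inducers and inhibitors and CYP1A2 substrates within 14 days of registration", with no strength limit, and then defers to the body: "Please refer to the full protocol text for a complete description of the eligibility criteria and treatment plan".

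**The concern.** Sites apply 3.3.7 at registration and 8.1 during treatment, so the protective limits should be complete in those sections.

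The 20 mg rule is a fixed target, not a step down. It protects most at the full dose and not at all at the lowest one. Yet a patient on 20 mg has usually been reduced twice for toxicity and has no level left below. That state is reachable: under 8.2.2.1 an episode of grade 2 or 3 diarrhea costs one cobimetinib level, and 1.6.3 reports diarrhea in 56.7% of patients on the combination in the phase III melanoma trial (all grades; the document gives no figure for two reductions).

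The contraception rule names a weakness of hormonal methods and then accepts two methods that share it. What is at stake is fetal exposure. The study calendar requires pregnancy tests only before registration and before treatment starts. None is scheduled on treatment, so contraception is the main continuing safeguard.

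For inducers the stake is loss of cobimetinib exposure. Section 10.2 says that a strong inducer "may decrease cobimetinib systemic exposure by more than 80% and reduce its efficacy". It gives no figure for a moderate one.

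**Working it through.** There is no sample size, power or error-rate figure to reproduce here. The check is dose arithmetic plus a comparison of sections.

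**1. The 20 mg rule.** Inputs: dose levels 60, 40 and 20 mg (8.2.1); target 20 mg (8.1.9). Reduction = (current dose − 20) / current dose. The rise in exposure that this exactly offsets = current dose / 20, if exposure is proportional to dose (1.7.2 states this up to 80 mg).

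| Current dose | Reduction | Rise offset |
|---|---|---|
| 60 mg | (60 − 20)/60 = 67% | 60/20 = 3.0-fold |
| 40 mg | (40 − 20)/40 = 50% | 40/20 = 2.0-fold |
| 20 mg | (20 − 20)/20 = 0% | 20/20 = 1.0 (none) |

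The 0% in the last row needs no pharmacokinetic assumption. The resulting exposure does. If a moderate inhibitor multiplies exposure by k, exposure relative to the patient's own previous dose is k × 20 / previous dose. The documents give no k for moderate inhibitors, only 6.7 for a strong one (10.2). For an assumed k of 2 to 4, the ratio runs from 40/60 = 0.67 to 80/60 = 1.33 for a patient coming from 60 mg, from 40/40 = 1.0 to 80/40 = 2.0 from 40 mg, and from 40/20 = 2.0 to 80/20 = 4.0 for a patient on 20 mg. This range illustrates the direction and is not evidence of its size.

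**2. Contraception.** Of the four listed methods, two are hormonal (oral and implantable). That pair counts as two methods, so it meets the literal rule with no non-hormonal component.

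**3. Inducers, section by section.**

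| Section | Strength barred or to be avoided | Limited to chronic use? | Names efavirenz or St. John's wort? |
|---|---|---|---|
| 3.3.7 | strong | yes | no |
| 8.1.10 | strong | yes in the rule; its listed examples are barred during treatment | no |
| 10.1 (vemurafenib) | strong | no | no |
| 10.2 (cobimetinib) | strong or moderate | no | yes, both |
| Summary page | no limit stated | no; registration only | no |

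A site that follows 8.1.10, checks a drug and finds a moderate inducer meets no bar in that section. It has to reach 10.2 to learn that the drug should be avoided. The documents do not grade efavirenz or St. John's wort individually.

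**4. Inhibitors in 3.3.7.** The adjective strong stands before inducers and is not repeated before inhibitors. The sentence can therefore bar all chronic CYP3A4 inhibitors, as the summary page does, or only strong ones, as 8.1.9 does. The text does not settle which.

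**The case against.** The best case for the plan is that its rules form tiers: chronic strong agents are prohibited, and moderate ones are to be avoided under 10.2, which is protocol text and applies throughout treatment. Section 8.1.10 also asks sites to check every drug for induction. This stands against a claim of contradiction. A reader might infer that 10.2 and 8.1.10 conflict, or that the protocol permits moderate inducers; the documents support neither. What remains is that the operative sections state a weaker limit than the drug information.

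A reader might also infer that chronic moderate inhibitors are allowed. That is not supported: 3.3.7 may already bar all chronic inhibitors, 8.1.9 admits moderate ones only briefly and when unavoidable, and 10.2 says to avoid them. Only the ambiguity in 3.3.7 stands.

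On the 20 mg rule, the gap needs two events together: a patient at the lowest level and an inhibitor that cannot be avoided. Exposure is capped at 14 days, the toxicity rules in 8.2.2 still operate, and the study chair can be asked. All of this narrows the gap. None of it tells a site what to do when the instructed reduction is zero.

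On contraception, 3.1 is guidance, the demand for two methods is itself a mitigation, and physicians are asked to discuss the choice. That is fair, but the discussion sets no minimum.

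Appendix V (patient handout and wallet card) and the consent pages are not in the text reviewed, so patient-facing instructions cannot be judged absent. The body cites the handout as optional, so it would not amend 8.1.

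**Conclusion.** The point holds as a set of wording gaps with a bearing on patient safety.

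- **20 mg rule:** a 0% reduction at the lowest level, certain from the text. The patient's only protection is the unavoidable condition, the 14-day cap and the general pointer to the brochure or study chair. The size of the exposure rise rests on an assumed k and on dose proportionality.
- **Contraception:** two hormonal methods satisfy the rule, although the same section warns about hormonal methods. This is certain from the text.
- **Inducers:** a lesser matter of alignment between sections. The loss of more than 80% in 10.2 applies to strong inducers only and should not be carried over to moderate ones.
- **Inhibitors in 3.3.7:** an ambiguity to resolve, not a demonstrated gap.

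The number of patients affected is not given and is not estimated. A reader might infer from the wording on reduced efficacy in 10.2 that the primary response rate would be biased or the two-stage design weakened. The documents give no basis for that: there is no moderate-inducer effect size and no expected frequency of use.

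**What to change.** 1. In 8.1.9, add: *For a patient already receiving cobimetinib 20 mg, use an alternative to the inhibitor or hold cobimetinib while it is given.* A hold of up to 14 days, even if it adjoins the 7-day break, totals 14 + 7 = 21 days. That is within the 28-day limit in 8.2, so it would not by itself force discontinuation.
2. In 3.1, require at least one of the two contraceptive methods to be non-hormonal.
3. Extend 3.3.7 and 8.1.10 to strong or moderate CYP3A4 inducers, and add the agents named in 10.2 to the examples in 8.1.10.
4. In 3.3.7, state whether the strength qualifier applies to CYP3A4 inhibitors as well as inducers.

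The cost is a wording amendment, with no new procedures or data. A few patients would have to switch a drug, interrupt cobimetinib briefly or add a contraceptive method, and a few might be excluded.
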